2.6 Safety Analyses

Safety endpoints will be summarized with descriptive statistics. All safety summaries and analyses will be performed using the safety population.

Prior and Concomitant medications will be coded by the World Health Organization (WHO) Drug Dictionary version September 2012.

Adverse Events and Medical History will be coded using MedDRA version 15.1.

2.7 Statistical/Analytical Issues

2.7.1 Adjustments for Covariates and Examination of Subgroup Analyses

Summaries with descriptive statistics and frequency counts for change in migraine days will be provided for the subgroups indicated below. A forest plot will also be created for subgroup analyses and will display treatment differences. The subgroups will be

- Calculated baseline migraine days (<9 days vs. ≥9 days)
- Sex
- Race (White, Black or African American, Other)
- Age Group (\leq 35 yrs, \geq 35 yrs)
- Age Group at Diagnosis of Migraine (≤21 yrs, >21 yrs)
- Duration of Migraine at Baseline (≤15 yrs, >15 yrs)

2.7.2 Handling of Dropouts or Missing Data

Summary statistics will be reported based upon observed data except for the diary data, which will utilize the imputation outlined below. Additionally, if the start date of an AE or concomitant medication is incomplete or missing, it will be assumed to have occurred on or after the intake of trial medication, except if an incomplete date (e.g., month and year) clearly indicates that the event started prior to treatment.

Subjects who do not complete the eDiary daily will have missing data. It is expected that most missing diary data will be sporadic.

Missing Headache End Date and Time

If the end date and time for a headache recorded in the eDiary is missing the headache end date will be set to the earlier of 23:59 on the day before the next reported headache or 23:59 on the last entry reported into the diary (i.e. the last evening report or if no evening report was completed after the start of the headache 23:59 on the day the headache started). Headaches that are not reported as stopped by the subject are missing the answers to the questions that allow for the determination of whether the headache was a migraine or not. In this population most headaches are migraines. Hence, these headaches with missing 'end' information will be classified as migraines.

Missing Data Rule 1

If the eDiary has been completed at least 21 days in a 28 day interval, then a normalization procedure will be used. The results will be normalized to 28 days by multiplying the observed results by the inverse of the completion rate (e.g. if a subject does not complete the eDiary on 5 days they will have completed the diary on 82% of the days and the normalized results will be the observed results times 1.22).

Missing Data Rule 2

If the eDiary has been completed on less than 21 days in the 28 day interval then the results for the 28 day interval will be a weighted function of the observed data for the current four week interval and the results from the previous interval. The weights will be proportional to how many days the diary was completed and will provide greater weight for higher completion rates. Specifically, the results will be derived as

$$28 (W X_c + (1 - W) X_p),$$

where W is the number of days the diary was completed/20, X_c is the available average daily results for the current interval and X_p are the average imputed daily results for the previous interval.

Unless it is stated otherwise all primary and secondary analyses will use both Missing Data Rules 1 and 2, as appropriate. For the exploratory analyses, only Missing Data Rule 1 will be used and the denominators for will reflect the number of subjects who completed the eDiary 21 or more days in the 28 day interval.

Sensitivity Rule

The primary endpoint and key secondary endpoints will also be analyzed using a modification to Missing Date Rule 2 to better understand the robustness of the selected algorithm. The analysis replaces X_p with X_b , where X_b are the baseline average daily results, if the subject withdrew from the study due to an adverse event, study burden, lack of efficacy or worsening of study indication or if the subject died.

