2.2.2 Migraine and Headache Endpoints

In the statistical analysis plan the term headache will encompass both headaches and migraine headaches. Migraine headaches (migraines) are a subgroup of the headaches with the characteristics outlined below. In this way all migraines are headaches but not all headaches are migraines. Migraine and headache data will be collected through week 48. Headache episodes will be self-reported by the subject. An episode is a single headache event which lasts at least 30 minutes, as defined by the subject reported start and end time. The migraine and headache endpoints will be summarized in four week, twelve week and the twenty-four week intervals. Specifically, migraine and headache endpoints will be summarized for the four week intervals: Weeks 1-4, 5-8, 9-12, 13-16, 17-20, 21-24, ... 44-48, the twelve week intervals 1-12, 13-24, 25-36, 37-48, and Weeks 1-24, 25-48 as outlined in Section 2.3. The results from Weeks 1 to 12 will be used for the primary analysis.

For this trial, migraines are defined using the definition of migraine without aura and probable migraine without aura as outlined by the International Headache Society. These definitions do not take the presence of aura into account. Subjects will report if they experienced aura with their headache. Hence, in the rare case of aura that does not develop into a migraine, this will not be classified as a migraine but a headache that meets the definition of a migraine without aura will be considered a migraine regardless of if aura was present or not.

Migraine Day

A migraine day is defined as any day with a headache that meets the migraine or probable migraine characteristics as outlined in the International Headache Society (IHS), ICHD II 2004-II, Section 1.1 and 1.6. Specifically, a migraine is defined as a self-reported headache that:

- 1. Lasted 4-72 hours
- 2. Had at least 2 of the following
 - a. Unilateral location
 - b. Pulsating quality
 - c. Moderate or severe pain intensity
 - d. Aggravation by or causing avoidance of routine physical activity

3. Had at least 1 of the following

- a. Nausea and/or vomiting
- b. Photophobia and phonophobia

A probable migraine is a headache that meets only 2 of the above criteria. These characteristics will be summarized for each 4-week interval.

Frequency, Change and Percent Change of Migraine Days / Headache Days

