The frequency of migraine days is the number of migraine days within four week intervals and the average four week frequency in twelve and twenty-four week intervals. Change from baseline is the difference in frequency between baseline and the counts within these four week intervals. The 12 and 24 week change is the difference in the frequency between baseline and the average of the, 4 week intervals. The percent change is 100 times the ratio of the change and the baseline frequency. Similar measures will be produced based upon headache frequency.

Migraine/ Headache Responder Rate

Three responder rates will be utilized: 50%, 75% and 100%. A responder is a subject who achieves a \geq 50% reduction, \geq 75% reduction, or 100% reduction in migraine days, respectively. These reductions will be evaluated by comparing the baseline frequency of migraine days to the migraine frequency in four week intervals.

Results from the four week intervals will be averaged to produce 12 and 24 week responder endpoints. A responder will be a subject who achieves the specified percent reduction in migraine headache days when response rates for each of the four week intervals are averaged.

Migraine Hours / Headache Hours

Migraine hours are the sum of the duration of migraines within four week intervals, and the average four week duration within 12 and 24 week intervals. Headache hours are similarly defined but include all headaches. Subjects with no migraines/headaches will have a duration of zero.

Migraine Attack / Headache Episode

A migraine attack is defined as 1 continuously recorded migraine. One attack may result in multiple migraine days. Headache episodes are similarly defined.

Migraine / Headache Severity

Headache severity will be collected on a 3 point scale: mild pain, moderate pain, severe pain. The percent of migraines and headaches with severe pain will be summarized. Subjects with no migraines/headaches will be included with a rate of zero.

Acute Medication Usage

The percent of migraines and headaches with acute medication usage as recorded in the eDiary will be summarized. Subjects with no migraines/headaches will be included with a rate of zero.

Acute Migraine Medication Usage

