The number of days within 4 week intervals that subjects used acute migraine medication (i.e. triptan or ergotamine) will be summarized in 4, 12 and 24 week intervals. The 12 and 24 week results will be the average of the individual 4 week results that make up those wider intervals (e.g. the secondary endpoint of Weeks 1-12 will be the average of the Weeks 1-4, 5-8 and 9-12 results). The change from baseline for these measures will be the difference between the baseline and post baseline interval.

Percentage of subjects with a migraine on the day after dosing

The percent of subjects with a migraine on the day after first dose will be summarized.

eDiary Reported Medication Usage

The percent of days per 28 days with medication usage will be summarized overall and by the type of medication used.

Average Migraine / Headache Length

The length of each migraine attack is the average of the duration of each migraine attack within a four week intervals. Headache hours are similarly defined but include all headaches. Subjects with no migraines/headaches will have a duration of zero.

Time to First Migraine

Time to the first migraine after dosing will be analyzed based upon the migraine data entered into the eDiary.

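### When a second headache is reported on the same day, the SAP's rule for a missing headache end time puts the end before the start, giving negative durations in migraine and headache hours and in average attack length

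*SAP*

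**What the plan says.** SAP 2.7.2, under the missing headache end date and time rule, sets the end to the "earlier of 23:59 on the day before the next reported headache or 23:59 on the last entry reported into the diary". A parenthesis explains the second option. The last entry means the last evening report or, "if no evening report was completed after the start of the headache 23:59 on the day the headache started". The same paragraph then settles classification: "these headaches with missing 'end' information will be classified as migraines".

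Two endpoints in SAP 2.2.2 use duration directly. For hours: "Migraine hours are the sum of the duration of migraines within four week intervals"; headache hours are built the same way from all headaches. For average length: "The length of each migraine attack is the average of the duration of each migraine attack within a four week intervals". SAP 2.2 lists hours among the other secondary endpoints and average length among the exploratory ones. SAP 3.4.4 reports hours with confidence intervals for the treatment difference, and SAP 3.4.5 does the same for average length in 4-week intervals. Neither is in the testing sequence of SAP 2.7.5.

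Protocol 13.3.2 covers missing diary days but has no rule for a missing headache end time, so the SAP text stands alone.

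**The concern.** The rule seems meant to stop an unclosed headache from running into the next one, and it does so by stepping back a whole calendar day. That works only if the next headache falls on a later date. If both start on the same date, stepping back a day goes past the start of the headache being closed.

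The rule does cover this case, but it returns an impossible value. The start-day fallback does not help, because it sits inside the explanation of the last-entry option and taking the earlier of the two options discards it. Neither document bars two headaches on one day, requires the end to be at or after the start, or gives a same-day exception.

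At stake are the duration summaries: a negative entry takes real hours off a subject's total. A programmer would probably notice. Without a written rule, though, the choice between dropping, zeroing or truncating the entry would be unplanned, and it might be made after the unblinding that follows the last Week 24 visit (SAP 1.4 and 2.7.3).

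**Working it through.** The plan gives no figure for this rule, so there is nothing to reproduce. The check is to apply the rule literally.

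**Inputs (SAP 2.7.2)**
- S = recorded start of the unclosed headache, on day D.
- A = 23:59 on the day before the next reported headache.
- B = 23:59 on the day of the last evening report or, if none followed the start, 23:59 on day D.
- Imputed end E = the earlier of A and B. Duration = E - S.

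**Same-day case, in general**
- If the next headache is also on day D, A = 23:59 on D-1.
- B is 23:59 on D or later, so B is after A and E = A every time.
- S is at or after 00:00 on D, so E is before S every time.
- Duration = -(clock time of S + 1 minute). The time of the second headache and the date of the last diary entry do not matter.

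**Numbers**
- Start 14:00 Day 10, next headache 20:00 Day 10: E = 23:59 Day 9. Duration = -(14 h 0 min + 1 min) = -14 h 1 min.
- Earliest start, 00:00: duration = -1 min.
- Start 23:58, next headache 23:59: duration = -(23 h 58 min + 1 min) = -23 h 59 min.

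**Other cases, same 14:00 Day 10 start**
- Next headache Day 11: E = 23:59 Day 10, duration +9 h 59 min.
- Next headache Day 13, last diary entry Day 12 or later: E = 23:59 Day 12, duration 48 h + 9 h 59 min = +57 h 59 min.
- No next headache, last evening report Day 10: E = 23:59 Day 10, duration +9 h 59 min.

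Only the same-day case gives an end before the start.

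**Size for one affected subject**, assuming a fully completed diary so that no normalization applies
- If the entry ended at the second headache's start, its duration would be 20:00 - 14:00 = +6 h.
- Difference in that 4-week total of migraine hours: 6 h - (-14 h 1 min) = 20 h 1 min.
- Difference in the Weeks 1-12 average of three intervals: 20 h 1 min / 3 = about 6 h 40 min.

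The size at arm level cannot be calculated, because the documents give no frequency for such entries.

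**The case against.** The strongest reply is that this is an edge case that may never arise. It needs the eDiary to accept a second headache on the same date while the first is still open, and neither document describes that behaviour. This stands as a limit on size. It does not clear the rule. The first option exists because a later headache can follow an unclosed one, and nothing confines that to later dates.

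The affected endpoints are also outside formal testing. And the same rule applies in every arm and at baseline, so some of any error would cancel in a between-arm comparison of change. Both points are fair and keep the severity low.

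Two stronger readings are tempting, and the documents support neither.
- A reader might infer that the start date drops out of the migraine-day count, which would reach the primary and responder endpoints. That assumes a program that lists days from start to end. The SAP's definition is different: "A migraine day is defined as any day with a headache that meets the migraine or probable migraine characteristics". The unclosed headache is classified as a migraine outright and its start date is recorded, not imputed, so that date is already a migraine day.
- A reader might infer that the entry breaks the minimum episode length. SAP 2.2.2 reads: "An episode is a single headache event which lasts at least 30 minutes, as defined by the subject reported start and end time". The test is on times the subject reported. An unclosed headache has no reported end, so the test does not apply to an imputed one.

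The exact repair is also partly a matter of choice. Treating the two entries as one continuing attack could be defended, and ending the first at the second's start can give a very short migraine (10 minutes for starts at 14:00 and 14:10). What is not a matter of choice is that the end must not precede the start.

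**Conclusion.** Wrong as written, low severity. In every same-day case the rule gives a negative duration, from about -1 min to -24 h, and no other part of either document corrects it. The effect is confined to migraine and headache hours and average attack length. For one subject it can be large: 20 h 1 min in a 4-week total in the worked example, measured against an end at the second headache's start.

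This conclusion rests on a literal reading of SAP 2.7.2, on the negative values being used without editing, and on the eDiary accepting a second same-day headache while one is open. The documents neither state nor bar the last of these. No arm-level effect is claimed, and none is shown on the primary or responder endpoints.

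**What to change.** Add to SAP 2.7.2 that the imputed end may never precede the recorded start, and that when the next headache starts on the same calendar day, the end is set to that headache's start time. Keep the existing rule in all other cases, where it gives the same result as now. For clarity, confirm in the same place that the start date of an unclosed headache counts as a migraine day.

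The cost is one sentence, a short confirmation and one line of derivation code. No new data are needed. It is best settled before the unblinding at Week 24.

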1.5 Sample Size

The planned sample size for this trial is 800 randomized and treated subjects. These subjects will be allocated into 4 treatment groups in a 1:1:1:1 ratio. Pair-wise testing of each ALD403 group vs. placebo will be performed. Two hundred subjects per group provides at least 95% power for each change in frequency of migraine days (Weeks 1-12) test individually assuming a treatment effect of at least 1 day and a common standard deviation of 2.7 days or less. Ninety percent power is retained for standard deviations up to 3 days. For the key secondary 75% responder

rates endpoints 95% power is achieved for the pair-wise comparisons assuming rates of 24% for placebo and 42% for ALD403. For the 50% responder rate endpoints 95% power is achieved for the pair-wise comparisons assuming rates of 50% for placebo and 68% for ALD403. For the percentage of subjects with a migraine on the day after dosing endpoint, 95% power is achieved for pair-wise comparisons assuming rates of 15% for placebo and 4% for ALD403.

These sample size calculations have been performed using Pass 2008 and are based upon t-tests and Chi-squared tests that should approximate the ANCOVA and CMH tests, respectively.⁴

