2.3 Trial Day

Trial endpoints will be reported within analysis windows or analysis intervals based upon the actual date of the assessment. Assignment of results to these time points is based upon the trial day. Trial day is defined as:

Trial day = date of assessment - date of treatment

Analysis Windows used to report non-diary endpoints are outlined in Table 2.

Table 2: Analysis Windows

Visit	Range	Target Day	If more than one which one is used
			for analyses
Screening	< Day 0		First value
Day 0	Day 0 to Day 7	Day 0	Day 0
Week 4	Day 8 to Day 42	Day 28	Closest to Target Day
Week 8	Day 43 to Day 70	Day 56	Closest to Target Day
Week 12	Day 71 to Day 98	Day 84	Closest to Target Day
Week 16	Day 99 to Day 126	Day 112	Closest to Target Day
Week 20	Day 127 to Day 154	Day 140	Closest to Target Day
Week 24	Day 155 to Day 182	Day 168	Closest to Target Day
Week 28	Day 183 to Day 210	Day 196	Closest to Target Day
Week 36	Day 211 to Day 273	Day 252	Closest to Target Day
Week 48	Day 274 to Day 357	Day 336	Closest to Target Day
Week 56	> Day 357	Day 392	Closest to Target Day

Note: If two observations exist with same distance to target day, use first observation.

For the eDiary data used to produce the migraine and headache endpoints the intervals specified in Table 3 will be used to collapse the daily data into 4, 12, and 24 week intervals. For these data baseline is defined as the 28 days starting on the day of the first diary entry.

Table 3: eDiary Headache/Migraine Endpoint Analysis Intervals

Diary			
Weeks	Trial Time	Comments	Endpoints
Baseline	The 28 days starting from the first eDiary entry		All eDiary related endpoints
1-4	Days: 0-27	Day 0 = First day of treatment	All eDiary related endpoints
5-8	Days: 28-55		All eDiary related endpoints
9-12	Days: 56-83		All eDiary related endpoints
1-12	Weeks 1-4, 5-8 and 9-12	Average of the 4 week intervals after imputation methods are applied	All Primary and Secondary eDiary related endpoints
13-16	Days: 84-111		All eDiary related endpoints
17-20	Days: 112-139		All eDiary related endpoints
21-24	Days: 140-167		All eDiary related endpoints
13-24	Weeks 13-16, 17-20 and 21-24	Average of the 4 week intervals after imputation methods are applied	All Primary and Secondary eDiary related endpoints
1-24	Weeks 1-4, 5-8, 9-12, 13-16, 17-20 and 21-24	Average of the 4 week intervals after imputation methods are applied	All Primary and Secondary eDiary related endpoints
25-28	Days: 168-195	1 11	All eDiary related endpoints

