2.5 Statistical Assessment of the Trial Objectives

Hypothesis testing will be performed for the primary endpoint: change from baseline in migraine days from Weeks 1-12. This endpoint will be calculated as outlined in Section 2.2.2 and will utilize the missing data rules provided in Section 2.7.2. The hypotheses tested are

$$H_o: \Delta_{plb} = \Delta_{403} H_a: \Delta_{plb} \neq \Delta_{403}$$

where Δ_{403} is the change in migraine days for subjects in the ALD403 treatment arm and Δ_{plb} is similarly defined for the placebo subjects. The change from baseline is expected to be negative as migraines are being reduced. While the test outlined above is two sided, as is the alpha level used for this study (i.e. 5%), clinically relevant results require a larger reduction of migraines on the ALD403 arms.

An ANCOVA model will be used to test for a difference between treatment arms. This model will include the change from baseline measure as the response variable. Treatment and the stratification variable: baseline migraine days (continuous covariate) will be the independent variables.

In addition, model based estimates including confidence intervals for the treatment differences will be used to summarize the results for the primary endpoint.

A sensitivity analysis of the change from baseline in migraine days will be performed using the sensitivity missing data rule provided in Section 2.7.2.

Secondary Efficacy Analyses

Summary statistics including confidence interval for the treatment differences will be used to summarize the results for the secondary endpoints. Testing will be performed for the key secondary endpoints and for the change in acute migraine medication days endpoint. For the key secondary endpoints (responder rates and percentage of subjects with a migraine on the day after dosing) this testing will utilize a CMH/extended CMH test. The tests will be stratified by the randomization stratification factor. The change in acute migraine medication day endpoints will be tested using an ANCOVA model similar to the one used for the primary endpoints: change from baseline measure as the response, treatment and baseline acute migraine medication days as independent variables. The time to first migraine analysis will be descriptively summarized based upon Kaplan-Meier methods.

Exploratory Analyses

Exploratory endpoints will be summarized with descriptive statistics by treatment group.

20

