2.7.5 Multiple Comparisons/Multiplicity

A serial procedure will be used to account for multiplicity of dose level for the primary endpoint and the secondary endpoints. This procedure will start with the 300 mg vs placebo comparison for the primary endpoint. If this is significant, testing will continue to a subset of the key secondary endpoints for 300 mg (first the Weeks 1-4 75% responder endpoint, then the Weeks 1-12 75% responder endpoint, and then the Weeks 1-12 50% responder endpoint). The procedure will then move on to the primary endpoint for the 100 mg group and subsequently to the same subset of key secondary endpoints as tested for the 300 mg dose. The procedure will then move on to the remaining key secondary endpoint for 300 mg and 100 mg (i.e., percentage of subjects with a migraine on the day after dosing). Only if all of these secondary endpoints reach statistical significance will the 30 mg group be tested.

Statistical testing will be conducted at the 5% alpha level.

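### The planned sensitivity analysis cannot change the Weeks 1-4 75% responder result, because the interval before Weeks 1-4 is already baseline

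*SAP*

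**What the plan says.** SAP 2.7.2 has two rules for incomplete diaries.

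- **Rule 1** applies with 21 or more completed days out of 28. The observed count is scaled up to 28 days, and no other interval is used.
- **Rule 2** applies with fewer than 21 days. The result is 28(W X_c + (1 - W) X_p), where W is completed days divided by 20, X_c is the current daily average, and "X_p are the average imputed daily results for the previous interval".

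The Sensitivity Rule, offered as a check on the robustness of the algorithm, covers the primary and key secondary endpoints. It makes one change: "The analysis replaces X_p with X_b , where X_b are the baseline average daily results". The change applies only to subjects who died or withdrew because of an adverse event, study burden, lack of efficacy or worsening of the indication.

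SAP Table 3 (section 2.3) defines Weeks 1-4 as Days 0-27. The one diary interval listed ahead of it is Baseline, defined as "The 28 days starting from the first eDiary entry".

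In SAP 2.7.5 the key secondary tests for 300 mg follow its primary test, "first the Weeks 1-4 75% responder endpoint". The same sequence is repeated for 100 mg.

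**The concern.** For Weeks 1-4 the previous interval is Baseline, so the quantity taken out and the quantity put in are the same. The SAP promises a robustness check on this endpoint that cannot move, whichever withdrawal reasons are listed.

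This matters because of the endpoint's place in the serial procedure. If it fails for 300 mg, nothing after it can be claimed: not the Weeks 1-12 responder endpoints, not 100 mg, not 30 mg. A report that set the main and sensitivity p-values side by side would show two identical numbers, and a reader could take agreement by construction for evidence of robustness. The SAP names no other sensitivity analysis for responder rates. The repeated-measures analysis in SAP 3.4.1 that is restricted to intervals with at least 21 diary days concerns change in migraine days.

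**Working it through.** **The plan's own figure.** SAP 1.5 has 800 subjects "allocated into 4 treatment groups in a 1:1:1:1 ratio", so 200 per arm, and states "95% power is achieved for the pair-wise comparisons assuming rates of 24% for placebo and 42% for ALD403". The alpha is 5% (SAP 2.7.5), two-sided (SAP 2.5). With the pooled chi-square formula:

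- mean rate = (0.24 + 0.42)/2 = 0.33
- z = [0.18 × √200 - 1.96 × √(2 × 0.33 × 0.67)] / √(0.24 × 0.76 + 0.42 × 0.58) = (2.546 - 1.303)/0.653 = 1.90
- power = 97.1%

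The stated 95% needs 175 per arm (186 with a continuity correction), so 200 meets it. This point does not affect the power figures.

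**The identity, by number of diary days d in Weeks 1-4.**

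- d = 21 to 28: Rule 1 applies and X_p does not appear.
- d = 20: W = 20/20 = 1, so X_p has weight zero.
- d = 0 to 19: Rule 2 uses X_p. The previous interval is Baseline, so X_p = X_b and the substitution changes nothing.

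**Enumeration.** Inputs were baseline diary days 25-28 (eligibility requires at least 25, SAP 1.2), baseline migraine days 4-14, d = 0-28, every migraine count from 0 to d, and withdrawn yes or no. That gives 4 × 11 × 435 × 2 = 38,280 cases. Changed imputed values: 0. Changed 75% responder classifications: 0.

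**Example at Weeks 1-4.** Baseline is 8 migraine days and the diary stops after 15 migraine-free days. W = 15/20 = 0.75. The main result is 28 × (0.75 × 0 + 0.25 × 8/28) = 2.0 days, a 75% reduction, so the subject is a responder. The Sensitivity Rule gives the same 2.0.

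**Where the rule does act.** Baseline is 8, Weeks 1-4 is 2 with a full diary, then the subject withdraws for a listed reason with no further diary. For Weeks 1-12 the main average is (2 + 2 + 2)/3 = 2.0, a 75% reduction. The sensitivity average is (2 + 8 + 8)/3 = 6.0, a 25% reduction.

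**What the main rules assume at Weeks 1-4.**

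- Rule 2 gives baseline the weight 1 - d/20, while the missing share is (28 - d)/28. At d = 15 these are 0.25 and 13/28 = 0.46.
- Filling the missing days at the baseline daily rate in the example above gives 0 + 13 × 8/28 = 3.71 days, a 54% reduction, so a non-responder.
- Under Rule 1, baseline 8, 21 diary days and 1 migraine day give 1 × 28/21 = 1.33 days, an 83% reduction. Baseline fill gives 1 + 7 × 8/28 = 3.0 days, a 62.5% reduction. The subject changes from responder to non-responder.

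**Illustrative size of a check that can move.** The documents give no missing-day rate. Two simulations with different assumed migraine distributions compared the main rules with baseline fill:

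| Missing days (assumed) | Difference, main to baseline fill, set A | Set B |
|---|---|---|
| 4% | 18.0 to 16.9 points | 16.9 to 16.0 |
| 8% | 17.3 to 15.0 | 16.6 to 14.5 |
| 12% | 16.7 to 13.3 | 16.0 to 13.2 |

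In set A at 8% missing, the rates with baseline fill are 14.7% and 29.7%. With 200 per arm the pooled rate is 0.222, and z = 0.150/√(2 × 0.222 × 0.778/200) = 3.6, p = 0.0003.

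**The case against.** **The main rule is already cautious here.** Rule 2 pulls every Weeks 1-4 diary with fewer than 21 days toward baseline, whatever the reason for the gap. The Sensitivity Rule would do so only for listed withdrawals and deaths. Under Rule 2 even a migraine-free subject needs 1 - d/20 ≤ 0.25, so at least 15 diary days, to count as a 75% responder. This stands: the check is empty because the main analysis already makes the substitution. It is not the whole answer, because W = d/20 gives missing days less than their share and Rule 1 is untouched.

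**The illustrative falls do not measure the empty substitution, whose effect is exactly zero.** This also stands. They come from replacing both rules. In a rough simulation at 8% missing, about 60-75% of the lost responders had 21 or more diary days and so fell under Rule 1.

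**Baseline fill is severe.** SAP 3.3.7 counts a day as missing, for the compliance summary, only if there was no diary contact and no headache. If the same definition governs Rule 1, scaling already adds migraine days to days with no recorded headache. This is a fair reason to label the run as conservative, but not a reason to keep a check that cannot move.

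**X_b might be read as the raw baseline count divided by 28.** The two values could then differ by up to 12% (28/25 = 1.12), but status changes in only 5 of 10,164 enumerated cells. The reading is strained, since X_c is an average over available days.

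**Stronger readings.** A reader might infer that the whole sensitivity plan is empty, or that the main Weeks 1-4 test is unsound. The documents support neither. The rule acts on the primary endpoint and the Weeks 1-12 responder endpoints, and the emptiness of a supportive check says nothing against the main test.

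**Conclusion.** The point holds, narrowly. For the Weeks 1-4 75% responder rate the Sensitivity Rule changes none of the roughly 800 classifications, so it cannot serve the purpose that SAP 2.7.2 gives it.

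This rests on two readings: that the interval before Weeks 1-4 is Baseline, which the SAP does not say in words but for which Table 3 leaves no other candidate, and that X_b is an average per completed diary day.

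The main test and the testing order stay valid. A reader might infer that a working check would overturn this step. Nothing here suggests so. The falls of about 1 to 3 points depend on assumed missingness and simulated main rates (about 19% against 36% in set A, not the planning 24% against 42%), and the dispersion of missing days behind set A is not recorded, so they show direction and rough size only. At 12% missing, a 13.3-point difference with an assumed placebo rate of 10-13% still gives 92-95% power with 200 per arm.

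The day-after-dosing endpoint has its own missing-data rule (SAP 3.4.3.1) and is outside this point.

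**What to change.** In SAP 2.7.2, state that the Sensitivity Rule cannot alter the Weeks 1-4 75% responder endpoint. For that endpoint only, replace it with one supportive run per dose, using the same stratified CMH test, in which

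migraine days = observed migraine days + (28 - days completed) × baseline daily rate

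for every subject with any missing day, including those with 21-27 diary days. Label the run as deliberately conservative.

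A separate run counting subjects with fewer than 21 diary days as non-responders is not needed. Eight missing days already add 8/28 = 28.6% of baseline, above the 25% that a 75% responder may retain, so all such subjects are non-responders in the proposed run.

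The cost is a few lines of SAP text and one extra CMH run per dose. The main test, alpha and testing order do not change. The downside is a supportive estimate that is more conservative than the main one.
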